1.1. Objectives, Endpoints, and Estimands

Objectives	Endpoints
Primary	

 To demonstrate that LY3209590 is noninferior to insulin degludec for the treatment of T1D in adults 	
 Change in HbA1c from baseline to Week 26
Key Secondary (Multiplicity Adjusted)	

 To demonstrate superiority of LY3209590 to insulin degludec 	
 Change in HbA1c from baseline to Week 26 Time in glucose range between 70-180 mg/dL (3.9-10.0 mmol/L), inclusive, measured by CGM 4 weeks prior to Week 26 Event rate of participant-reported, clinically significant nocturnal hypoglycemia (<54 mg/dL [3.0 mmol/L] or severe) during the treatment phase up to Week 52
Other Secondary	

 To investigate the effect of LY3209590 compared with insulin degludec in additional parameters of glycemic control 	
 Change in HbA1c from baseline to Week 52 Change from baseline to Weeks 26 and 52 in fasting glucose as measured by SMBG Glucose variability, measured by CGM 4 weeks prior to Weeks 26 and 52

Objectives	Endpoints
	
 • Time in glucose range between 70-180 mg/dL (3.9-10.0 mmol/L), inclusive, measured by CGM 4 weeks prior to Week 52 • Insulin dose at Weeks 26 and 52 
 ◦ basal ◦ bolus ◦ total, and ◦ basal/total insulin dose ratio

 • To compare the safety of LY3209590 to insulin degludec 	
 • Rate of composite of Level 2 and 3 hypoglycemia events during the treatment period • Body weight change from baseline to Weeks 26 and 52 • Time in hypoglycemia range with glucose <54 mg/dL (3.0 mmol/L), measured by CGM 4 weeks prior to Weeks 26 and 52 • Time in hyperglycemia range, defined as glucose >180 mg/dL (10.0 mmol/L), measured by CGM 4 weeks prior to Weeks 26 and 52

 • To compare treatment satisfaction and health-related quality of life between LY3209590 and degludec as assessed by patient-reported outcome questionnaires 	
 • DTSQ change from baseline to Weeks 26 and 52 • Change in SF-36 v2 acute form domain scores from baseline to Weeks 26 and 52
Tertiary	

 • To investigate the effect of LY3209590 compared with insulin degludec on other measures of efficacy, safety, and patient-reported outcomes 	
Efficacy
 
 • Percentage of participants achieving HbA1c <7% at Weeks 26 and 52 • Percentage of participants achieving HbA1c ≤6.5% at Weeks 26 and 52 • Change from baseline to Weeks 26 and 52 in fasting serum glucose as measured by a central laboratory

Objectives	Endpoints
	
Safety
 
 • Rate and incidence of Level 2 hypoglycemia events during the treatment period • Rate and incidence of Level 3 hypoglycemia events during the treatment period • Incidence of positive treatment-emergent antibodies of LY3209590
	
Patient-reported outcomes
 
 • Frequency of responses to “Basal Insulin Experience: Likelihood of incorporating into routine” at Weeks 26 and 52 • Frequency of responses to “Basal Insulin Experience: Preference” at Weeks 26 and 52 • Change in EQ-5D-5L from baseline to Weeks 26 and 52
To characterize the PK/PD of LY3209590	
 • LY3209590 PK and concentration response relationships to key safety and efficacy measures. • Potential intrinsic and extrinsic factors.

Abbreviations: CGM = continuous glucose monitoring; DTSQ = Diabetes Treatment Satisfaction Questionnaire; EQ-5D-5L = European Quality of Life Questionnaire; HbA1c = hemoglobin A1c; PK/PD = pharmacokinetics/pharmacodynamics; SF-36 v2 = Short Form-36 Version 2 Health Survey Acute Form; SMBG = self-monitored blood glucose; T1D = Type 1 diabetes mellitus.

Primary estimand (for primary objective)

United States registration

The *primary* clinical question of interest is below:

- What is the treatment difference between LY3209590 and insulin degludec in hemoglobin A1c (HbA1c) change from baseline after 26 weeks of treatment, in study-eligible participants with T1D treated with multiple daily injection (MDI) therapy, regardless of treatment discontinuation for any reason and regardless of initiation of rescue medication?

The **treatment-regimen estimand** will be used for the primary objective, and the attributes are described in the following table.

Treatment-Regimen Estimand Attributes	Description
Population	Targeted study population. See Section 3 for details.
Endpoint	HbA1c change from baseline to Week 26.
Remaining intercurrent events	None. The intercurrent events, treatment discontinuation for any reason, and initiation of rescue medication, are addressed by the treatment condition of interest attribute.
Treatment condition	The randomized treatment, regardless of treatment discontinuation, and use of rescue medications.
Population-level summary	Difference in mean changes between treatment conditions.

Abbreviation: HbA1c = hemoglobin A1c.

Rationale for the treatment-regimen estimand

The treatment-regimen estimand estimates how participants with T1D are treated in clinical practice and considers both efficacy and safety.

Registration for countries outside the United States

The *primary* clinical question of interest is below:

- What is the treatment difference between LY3209590 and insulin degludec in hemoglobin A1c (HbA1c) change from baseline after 26 weeks of treatment, in study-eligible participants with T1D treated with MDI therapy who adhere to the randomized treatment without an intercurrent event during the study treatment period?

The **efficacy estimand** will be used for the primary objective. This table describes the efficacy estimand attributes.

Efficacy-Regimen Estimand Attribute	Description
Population	Targeted study population. See Section 3 for details.
Endpoint	Hemoglobin A1c change from baseline to Week 26.
Remaining intercurrent event	None. The intercurrent event, treatment discontinuation for any reason, and initiation of rescue medication, are addressed by the hypothetical strategy; for example, the potential outcome for those participants if the intercurrent events have not occurred will be estimated.
Treatment condition	The randomized treatment.
Population-level summary	Difference in mean changes between treatment conditions.

Abbreviations: HbA1c = hemoglobin A1c.

The efficacy estimand supports the interpretation of the treatment effect as participants adhere to study treatment and is free from the confounding effect of rescue medications.

Secondary estimands for multiplicity-adjusted objectives

The superiority test in change from baseline to Week 26 (Visit 22) in HbA1c will also be based on the primary estimand described above.

The time in glucose range between 70 and 180 mg/dL (3.9 and 10.0 mmol/L), inclusive, measured by continuous glucose monitoring (CGM) in the 4 weeks prior to Visit 22 (Week 26) will use the treatment regimen estimated for US registration and the efficacy estimand for other countries.

Participant-reported, clinically significant nocturnal hypoglycemia (<54 mg/dL [3.0 mmol/L] or severe) is one of the safety measures for the study. The event rate will be based on all available data during the specific analysis period. The relative rate between randomized treatment groups will be used for treatment comparison.

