2.3.3. Overall Benefit Risk Conclusion

Considering the clinical data to date and measures taken to minimize risk for the participants in this study, the potential risks identified in association with LY3209590 are justified by the anticipated benefits that may be afforded to participants with T1D.

3. Objectives, Endpoints, and Estimands

Objectives	Endpoints
Primary	
To demonstrate that LY3209590 is noninferior to insulin degludec for the treatment of T1D in adults	
 Change in HbA1c from baseline to Week 26
Key Secondary (multiplicity adjusted)	
To demonstrate superiority of LY3209590 to insulin degludec	
 Change in HbA1c from baseline to Week 26 Time in glucose range between 70 and 180 mg/dL (3.9 and 10.0 mmol/L) inclusive, measured by CGM 4 weeks prior to Week 26 Event rate of participant-reported clinically significant nocturnal hypoglycemia (<54 mg/dL [3.0 mmol/L] or severe) during treatment phase up to Week 52
Other Secondary	
To investigate the effect of LY3209590 compared with insulin degludec in additional parameters of glycemic control	
 Change in HbA1c from baseline to Week 52 Change from baseline to Weeks 26 and 52 in fasting glucose as measured by SMBG Glucose variability, measured by CGM 4 weeks prior to Weeks 26 and 52 Time in glucose range between 70 and 180 mg/dL (3.9 and 10.0 mmol/L) inclusive, measured by CGM 4 weeks prior to Week 52 Insulin dose at Weeks 26 and 52 
 basal bolus total, and basal/total insulin dose ratio

To compare the safety of LY3209590 to insulin degludec	
 • Rate of composite of Level 2 and 3 hypoglycemia events during treatment period • Body weight change from baseline to Weeks 26 and 52 • Time in hypoglycemia range with glucose <54 mg/dL (3.0 mmol/L), measured by CGM 4 weeks prior to Weeks 26 and 52 • Time in hyperglycemia range defined as glucose >180 mg/dL (10.0 mmol/L), measured by CGM 4 weeks prior to Weeks 26 and 52
To compare treatment satisfaction and health-related quality of life between LY3209590 and degludec as assessed by patient-reported outcome questionnaires	
 • DTSQ change from baseline to Weeks 26 and 52 • Change in SF-36 v2 acute form domain scores from baseline to Weeks 26 and 52
Tertiary	

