9.3.3.2. Other Secondary Endpoints

Other secondary endpoints include various measures for efficacy, safety, and patient-reported outcome questionnaires.

Efficacy measures and patient-reported questionnaires will be analyzed using the EAS2 unless otherwise noted.

Safety measures will be analyzed using the SS regardless of LY3209590 or insulin degludec discontinuation and use of rescue medications.

Analysis details will be provided in the SAP.

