The study protocol contains a summary of the planned statistical analyses of the most important endpoints, including primary and key secondary endpoints. There are no changes to the analyses described in the protocol. This SAP includes the analysis details for efficacy, safety measures, patient-reported outcomes, and parameters based on continuous glucose monitoring (CGM). The analysis described in this SAP is primarily for the Clinical Study Report (CSR). Additional analysis will also be done for the Summary of Clinical Safety related to the Type 1 diabetes mellitus (T1D) indication. Details regarding these additional analyses are outlined in the Program Safety Analysis Plan (PSAP). Pharmacokinetic/pharmacodynamic (PK/PD) analyses will be conducted by the PK/PD group and will be described in the PK analysis plan. The specifications for tables, figures, and listings will be described in separate documents.

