The table below describes the definition of baseline and postbaseline observations for different analyses.

Analysis	Baseline Observations	Postbaseline Observations
HbA1c (treatment-regimen estimand)	Baseline is the last non-missing assessment prior to or on the day of first dose of study treatment.	Planned measurements at Week 26 (primary endpoint, Visit 22) and Week 52 (secondary endpoint, Visit 29) in EAS1. Use unplanned measurements (on the same visit day) if there are no planned measurements. A multiple imputation approach will be used to impute missing observations at Week 26 (Visit 22) and Week 52 (Visit 29).
HbA1c (efficacy estimand)	Baseline is the last non-missing assessment prior to or on the day of first dose of study.	Weeks 2, 4, 12, 16, 26, 36, and 52 (Visits 5, 7, 15, 17, 22, 25, and 29) in EAS2 for MMRM. All planned measurements at scheduled visits will be included. Use unplanned measurements (on the same visit day) if there are no planned measurements.
CGM parameters (treatment-regimen estimand)	Baseline will be derived from the data collected prior to the first dose of study treatment. A multiple imputation will be used to impute missing observations at baseline.	The CGM values 4 weeks prior to Week 26 (Visit 22) and Week 52 (Visit 29) in EAS1. A multiple imputation approach will be used to impute missing observations at Week 26 (Visit 22) and Week 52 (Visit 29). See detailed derivations in Appendix 6 (Section 6.6).
CGM parameters (efficacy estimand)	Baseline will be derived from the data collected prior to the first dose of study treatment.	The CGM values prior to Weeks 4, 8, 12, 16, 22, 26, 32, 36, 40, 44, 48, and 52 (Visits 7, 11, 15, 17, 20, 22, 24, 25, 26, 27, 28, and 29) in EAS2 for MMRM. See detailed derivations in Appendix 6 (Section 6.6).
Basal insulin dose	The baseline period is the screening/lead-in period prior to the initiation of study treatment. The following variables will be derived: 
• daily dose in U• weekly dose in U, and• dose in U/kg/day. See a detailed derivation of variables in Section 4.4.2.1.	All scheduled visits between Week 0 (Visit 3) and Week 52 (Visit 29) in EAS2 for MMRM. The following variables will be derived: 
• daily dose in U• weekly dose in U, and• dose in U/kg/day See a detailed derivation of variables in Section 4.4.2.1.

Analysis	Baseline Observations	Postbaseline Observations

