4.4.2. Supportive Secondary Endpoints

4.4.2.1. Other Efficacy Endpoints

The analysis of change from baseline for HbA1c at Week 52, fasting glucose by self-monitored blood glucose (SMBG) at Weeks 26 and 52, CGM (except for variability) parameters at Weeks 26 and 52 will be performed for both treatment regimen estimand and efficacy estimand.

For treatment regimen estimand, only participants with an observation at baseline or at the endpoint visit will be included in the analysis. The missing baseline will be imputed using multiple imputation under assumption of missing at random. Missing data at the endpoint visit will be imputed using either retrieved dropout or return-to-baseline multiple imputation approach determined by the criterion described for the primary efficacy endpoint in Section 4.3.2. ANCOVA analysis will be conducted similar to that for the primary endpoint. An additional term of baseline HbA1c stratum ($<8.0\%$, $\geq8.0\%$) will be added into the model for the endpoints other than HbA1c.

For efficacy estimand, participants with baseline and at least 1 post baseline observation will be included in the analysis. The longitudinal observations of actual and change from baseline in HbA1c up to Week 52 will be analyzed using the same MMRM model as for the efficacy estimand described in Section 4.3.2. The analyses of other continuous efficacy measures (insulin dose, fasting glucose, and CGM parameters) will use an MMRM model similar to that for the primary endpoint with an additional term of baseline HbA1c stratum ($<8.0\%$, $\geq8.0\%$). The variance-covariance structure in the MMRM models for fasting glucose from SMBG and insulin dose will be based on compound symmetry.

Additional analyses are as specified below.

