4.4.2.2. Other Safety Endpoints

The safety measures based on CGM data will be analyzed as described in Section 4.4.2.1.1. For other safety measures, the details are provided in Section 4.6.

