4.6. Safety Analyses

Safety measures include treatment exposure, AEs, vital signs, weight, hypoglycemia, laboratory measures, and immunogenicity. All safety analyses will be based on the Safety Analysis Set

(SS). Unless otherwise specified, the safety analysis period will include both the treatment period and follow-up period.

Percentages will be calculated using the SS as the denominator. For events that are sex-specific, the denominator and computation of the percentage will include only participants from the given sex. Unless otherwise noted, Fisher's exact test will be used for the treatment comparison and risk difference and 95% confidence intervals will be provided. Additionally, an odds ratio and 95% confidence intervals will be provided for selected tables in addition to the risk difference.

For continuous safety variables (for example, laboratory measures, vital signs, and weight), descriptive statistics for the observed and change from baseline at scheduled visits during the treatment and the follow-up period will be provided. For selected laboratory measures (that is, liver enzyme tests, lipid measures), observed values, change from baseline, and percentage change from baseline will be analyzed for the log-transformed values by the MMRM model using treatment, visit, and treatment by visit as fixed effects; baseline of the dependent variable as a covariate; and compound symmetry as the variance-covariance structure. The last postbaseline observation in the study will be analyzed by the ANCOVA model with the independent variables of treatment and baseline of the dependent variable.

The incidence and event rate of participant-reported and CGM-based hypoglycemia will be summarized by treatment and analysis period for different types of hypoglycemia. Analysis details are provided in Section 4.6.3.1.

The treatment-emergent analyses will use all data in the analysis period, including scheduled and unscheduled measurements. The safety analysis period for treatment-emergent analyses starts after the first dose and ends at the last visit in the study, including the safety follow-up period.

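### The protocol puts CGM time below 54 mg/dL and above 180 mg/dL on the Safety Analysis Set, but the SAP analyses both only on EAS1 and EAS2 and declares no change

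*SAP*

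**What the plan says.** Both documents place the two endpoints under the objective of comparing safety: "Time in hypoglycemia range with glucose <54 mg/dL (3.0 mmol/L), measured by CGM 4 weeks prior to Weeks 26 and 52" (SAP 1.1) and "Time in hyperglycemia range defined as glucose >180 mg/dL (10.0 mmol/L), measured by CGM 4 weeks prior to Weeks 26 and 52" (Protocol Section 3). For other secondary endpoints, Protocol 9.3.3.2 states: "Safety measures will be analyzed using the SS regardless of LY3209590 or insulin degludec discontinuation and use of rescue medications". The SS is the whole mITT population with every measurement (Protocol 9.2, SAP 3).

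The SAP takes a different route. Section 4.4.2.2 says "The safety measures based on CGM data will be analyzed as described in Section 4.4.2.1.1", and that subsection belongs to 4.4.2.1, Other Efficacy Endpoints. Section 4.4.2.1 says that analyses of CGM "parameters at Weeks 26 and 52 will be performed for both treatment regimen estimand and efficacy estimand", leaving out only the variability measures. The table in 4.1 gives the data source for the treatment-regimen estimand: "The CGM values 4 weeks prior to Week 26 (Visit 22) and Week 52 (Visit 29) in EAS1", with multiple imputation. For the efficacy estimand it names EAS2 with an MMRM. Neither CGM row mentions the SS.

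Elsewhere the SAP says "All safety analyses will be based on the Safety Analysis Set" (4.6) and "There are no changes to the analyses described in the protocol" (Section 1). Section 4.9 repeats that there are no changes.

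**The concern.** A protocol rule for safety endpoints has been replaced by efficacy analysis sets without a declared deviation, and the SAP contradicts itself on which set applies.

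Two things are at stake. First, both efficacy sets leave out dosed participants who stopped because they should not have been enrolled. A participant found after dosing to breach exclusion 10 (repeated severe hypoglycemia) or 11 (hypoglycemia unawareness) could plausibly spend more time below 54 mg/dL than others. That participant would count in the diary hypoglycemia and adverse event analyses but not in these two CGM comparisons. Second, the EAS2 analysis estimates what would have happened without discontinuation or rescue. That is a legitimate efficacy question, but it is not the one the protocol asks of a safety measure.

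**Working it through.** **Step 1: the sets side by side (SAP 3).**

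| | SS | EAS1 | EAS2 |
|---|---|---|---|
| People | mITT | mITT less those who stopped study treatment because of inadvertent enrollment | as EAS1 |
| Data | all | all, whatever the treatment or rescue status | to last dose +10 days (LY3209590) or +1 day (degludec), or to first rescue if earlier |
| Where the two CGM times are assigned to it | Protocol 9.3.3.2; SAP 4.6 by its general rule | SAP 4.1 and 4.4.2.1 | SAP 4.1 and 4.4.2.1 |

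EAS1 therefore differs from the SS in people only. EAS2 differs in people and in data. The EAS1 analysis further requires an observation at baseline or at the endpoint visit (SAP 4.4.2.1), but that is a modelling rule and not part of the set.

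**Step 2: is the protocol assignment clear?** The endpoints sit under the safety objective, and the safety sentence in Protocol 9.3.3.2 carries no exception; the qualifier there applies to the sentence on efficacy and questionnaires. Protocol 8.1 names time in range 70 to 180 mg/dL as the only CGM efficacy measure. SAP 4.4.2.2 itself calls the endpoints safety measures, and SAP 3 describes EAS2 as serving efficacy measures. Two other endpoints under the same objective, the Level 2/3 event rate and body weight, stay on the SS (SAP 4.6.3.1.1, 4.6.3.4).

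**Step 3: does another analysis close the gap?** The sensitivity analyses that restore inadvertently enrolled participants cover the primary endpoint (SAP 4.3.3.2) and the key secondary endpoints (4.4.1.3), not these two. The CGM sensitivity analyses in Appendix 6 relax data completeness, not the population. CGM-derived Level 2 events (4.6.3.1.2) fall under 4.6 and so on the SS, but they measure event rate, incidence and episode duration, not percentage of time.

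**Step 4: size for the people left out.** The documents give neither the number of inadvertent enrollees nor a mean time below 54 mg/dL, so all of these inputs are assumed:
- inadvertent enrollees: 0.5% to 2% of 670, or 670 × 0.005 = 3.4 to 670 × 0.02 = 13.4 over both arms;
- mean time below 54 mg/dL among those retained in an arm: 0.6%;
- k = 1 to 5 excluded participants in one arm of 335, each running at x = 2% to 4%.

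Shift in that arm's mean = k(x − 0.6)/335.
- Low: 1 × (2 − 0.6)/335 = 0.0042 percentage points, or 0.0042/0.6 = 0.7% of the mean.
- High: 5 × (4 − 0.6)/335 = 0.0507 percentage points, or 0.0507/0.6 = 8.5% of the mean.

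The shift in the treatment difference is one arm's shift minus the other's. It is zero if the same number, with the same values, is excluded from each arm.

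**Step 5: size for the EAS2 cutoff.** The plan's own figure reproduces: 335 × (1 − 0.15) = 284.75, against 284 completers per arm stated. If 5%, 10% or 15% of an arm stop treatment (an assumed range; 15% is the planned dropout at Week 26), EAS2 truncates 335 × 0.05 = 17, 335 × 0.10 = 34 or 335 × 0.15 = 50 participants. This is an upper count of what the SS could recover, because those who leave the study have no later CGM data in any set.

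**The case against.** The strongest reply is that the substance of the protocol rule is already met. EAS1 keeps all measurements regardless of discontinuation or rescue, as the SS does, and the SAP applies it to both endpoints at both weeks. This stands. It reduces the EAS1 gap to the inadvertent enrollees, and a reader should not infer that the plan discards all data after stopping. Even EAS2 keeps readings to +10 or +1 days unless rescue comes first.

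Nor do the excluded participants disappear from every CGM hypoglycemia comparison, as a reader might infer. The CGM Level 2 event analyses include all data and belong to the SS section. The contrast with diary hypoglycemia is also limited, because the diary treatment period ends at the same +10/+1 days after early stopping (SAP 4.1). The contrast concerns people, not follow-up.

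The mechanism is weak for early stoppers. The endpoints use the 4 weeks before Weeks 26 and 52, so someone stopped well before then would mostly add off-treatment or imputed values. This limits the size, but the protocol rule applies regardless of discontinuation.

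Time below, within and above range come from the same readings, so one population for all ranges is defensible. That argues for keeping EAS1 and EAS2 beside an SS analysis, not for omitting the SS.

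Finally, the list of safety measures in Protocol 9.3.5 does not name CGM times, Protocol 9.3.3.2 leaves details to the SAP, and SAP 4.1 allows exceptions to the SS where noted. These points soften the conflict without removing it. Leaving details to the SAP does not extend to changing the analysis set, the SS sentence in SAP 4.6 has no exception, and 4.9 declares no deviation. The program safety plan may contain more, but it is not among the documents.

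**Conclusion.** The point holds as an undeclared conflict between the protocol and the SAP, and within the SAP, over the analysis set for two safety endpoints. It should be fixed. It does not touch the primary or key secondary analyses.

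The numerical effect is likely small. The 0.004 to 0.05 percentage points rests entirely on assumed inputs and places every excluded participant in one arm; no effect on the treatment difference has been shown. A reader might infer that the plan hides a hypoglycemia signal or favours one arm. The documents do not support that: they give no count of inadvertent enrollees, no sign that any breached exclusion 10 or 11, and no reason to expect imbalance. The 15% dropout is not a measure of lost safety data either, since participants who stay after stopping treatment remain in EAS1 unless they were inadvertently enrolled.

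**What to change.** In SAP 4.4.2.2 and the CGM rows of the 4.1 table, add an analysis of both endpoints at Weeks 26 and 52 on the SS, as the protocol-specified safety analysis. It should use all CGM data regardless of discontinuation or rescue, with the EAS1 ANCOVA and imputation. Keep the EAS1 and EAS2 results alongside it, so that all glucose ranges can also be read on one population. Carry over the imputation method chosen under EAS1: a few extra retrieved dropouts could otherwise cross the fewer-than-8 threshold in SAP 4.3.2, and the two runs would differ in more than population.

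If the sponsor prefers EAS1 and EAS2 alone, SAP 4.9 should declare and justify the deviation, and 4.1 and 4.6 should be reconciled with 4.4.2.1 and 4.4.2.2.

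The cost is a short SAP edit and one extra run of an existing program. The small downside is that complementary glucose ranges would be shown on slightly different sets.
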